APPENDIX K

HEDGEHOG PATHWAY ANTAGONISTS IN USE OR WITH POTENTIAL INTERACTION OF THE HEDGEHOG PATHWAY

The table below lists experimental compounds in columns under the designation of specific target of the Hedgehog pathway.

This is not necessarily a complete list; other medications may also interact with Hh pathway.

| Target | Inhibitor |
|-----------|----------------|
| Gli | ATO |
| Gli | GANT58, 61 |
| Gli | HPI 1-4 |
| Gli | Glabrescione B |
| Gli | JQ1 |
| РКА | Imiquimod |
| RARβ/RARγ | Tazarotene |
| aPKC | PSI |

Abbreviations: Hh, Hedgehog; BCC, basal cell carcinoma; PKA, protein kinase A; aPKC, atypical protein kinase C ν/λ ; RAR β /RAR γ , retinoic acid receptor β/γ ; ATO, arsenic trioxide; PSI, specific peptide inhibitor; Gli, Gli transcription factors.

Senhwa Biosciences, Inc.

Protocol CX-4945-07 Version 6.0

Approved by

[name], Chief Medical Officer

Date

CRF	Case report form, paper or electronic
CRO	Contract research organization
CSR	Clinical study report
CTCAE	Common terminology criteria for adverse events
DLT	Dose limiting toxicity
ECG	Electrocardiogram
ECOG	Eastern Cooperative Oncology Group
eCRF	Electronic Case Report Form
Hh	Hedgehog
mBCC	Metastatic basal cell carcinoma
MedDRA	Medical Dictionary for Regulatory Activities
NCI	National Cancer Institute
ORR	Objective response ratio
РТ	Preferred Term
RDI	Relative dose intensity
RECIST	Response Evaluation Criteria in Solid Tumors
RP2D	Recommended Phase II Dose
SAE	Serious adverse event
SAP	Statistical Analysis Plan
SD	Standard deviation
SDTM	Study Data Tabulation Model
SOC	System organ class
TEAE	Treatment-emergent adverse event
WHO-DD	World Health Organization – Drug Dictionary

1. INTRODUCTION

This Statistical Analysis Plan (SAP) is based on the study Protocol version 6.0 dated 06 April 2022.

This document provides additional details concerning the statistical analyses outlined in the protocol and reflects any changes to the protocol from any amendments. This plan will not repeat all the definitions given in the protocol but will provide further details of the summaries and analyses planned therein. Any deviations from the analysis plan, including any after the time of database lock, will be documented as such in the study report.

2. STUDY OBJECTIVES

Primary Objective: The primary objective of this study is to determine the recommended phase II dose (RP2D) and schedule of CX-4945 when administered orally twice daily for 28 consecutive days, in a 4-week (28 days) cycle, in patients with locally advanced or metastatic basal cell carcinoma (BCC).

Secondary Objectives:

- To establish the safety and tolerability of CX-4945 in this patient population.
- To assess preliminary evidence of antitumor effects in this patient population by documentation of objective responses using standardized criteria.
- To evaluate the effect of CX-4945 treatment on the Hedgehog (Hh) signaling pathway using qRT-PCR in tissue from patients with locally advanced BCC obtained at baseline and following CX-4945 treatment.

3. STUDY DESIGN

This is an open-label, multicenter, treatment-duration-increment Phase I run-in study followed by two expansion cohorts in patients with advanced basal cell carcinoma, to evaluate the safety, pharmacodynamic and preliminary antitumor activity of CX-4945. All patients will receive CX-4945 until evidence of progression, intolerable toxicities most probably attributable to CX-4945, or withdrawal from the study.

This study population will consist of patients ≥ 18 years old with a histologically confirmed diagnosis of advanced BCC (metastatic BCC [mBCC] or locally advanced BCC defined as follows) which has progressed on smoothened inhibitor or that are intolerant to smoothened inhibitor. Patients with mBCC are required to have histologic confirmation of a distant BCC metastasis (e.g., lung, liver, lymph nodes, or bone). Patients with locally advanced BCC are required to have disease that is considered inoperable or to have a medical contraindication to surgery. Patients with nevoid BCC syndrome (Gorlin syndrome) may enroll in this study but must meet the criteria for locally advanced or metastatic disease listed above.

In the phase I treatment-duration-increment part of the study, the 28-day continuous dosing of CX-4945 [1000 mg twice daily] will be explored. Dose cohort will initially include a minimum of 3 patients. A standard 3+3 design will be used.

- If no DLTs are seen in the 3 patients, the treatment-duration-increment part will be closed and the expansion cohorts will be opened.
- If 1 patient out of 3 experiences a DLT, up to 3 additional patients will be recruited (for a maximum of 6). If there are < 2/6 patients with DLT, this will be declared the dose for the Recommended Phase II Dose (RP2D), Phase I will be closed and the expansion cohorts will be opened.
- If 2 out of 3, or 2 out of 6, patients experience DLT, the previous Phase I oral dosing regimen of 1000 mg BID (total daily dose 2000 mg) for 21 days followed by 7 days of rest will be selected for the expansion cohorts.

The expansion cohorts will include 10 patients with locally advanced BCC and 10 patients with metastatic BCC.

During the treatment-duration-increment part, the first patient enrolled at the 28-day continuous dosing schedule must receive \geq 75% planned doses with no observed DLTs before a second patient and a third patient are treated one week apart in that cohort. If no patient in the cohort experiences a DLT after the completion of Day 28 of the final patient in the cohort, then the Expansion Cohorts may proceed with the 28-day continuous dosing schedule.

Patients that have experienced a DLT may be offered the option to continue at the previous Phase I oral dosing regimen of 1000 mg bid (total daily dose of 2000 mg) for 21-day followed by 7 days of rest if this is considered safe by the Investigator and the Sponsor.

4. HARDWARE AND SOFTWARE

Statistical analysis will be performed following IQVIA Biotech standard operating procedures and on the IQVIA Biotech computer network. All statistical analysis will be performed using SAS Version 9.4 or later with program code prepared specifically for the project by qualified IQVIA Biotech statisticians and SAS programmers.

The SAS programs will generate rich-text-formatted (RTF) output with the "RTF" extension using the SAS Output Delivery System (ODS). Datasets will be created and taken as input to validated SAS programs to generate report-ready tables, listings, and figures. Each output display will show the names of the data sets and SAS program used to produce it.

5. DATABASE CLOSURE

After completion of all data review procedures, validation of the project database, and approval of the data review document by the study sponsor, the clinical database will be closed. Any change to the clinical database after this time will require written authorization, with explanation, by the Sponsor and the IQVIA Biotech Biostatistician.

6. SAMPLE SIZE DETERMINATION

In the treatment-duration-increment part of the study, a 3+3 study design will be utilized, therefore approximately 3-6 patients will be enrolled to define the RP2D.

In the expansion part of the study, a total sample size of 20 patients is proposed; 10 patients with local advanced BCC and 10 patients with metastatic BCC. Assume that CX-4945 is of no interest if its true response is 5% or lower, the proposed sample size for each sub-population will provide an 80% confidence interval of (5.5%, 45.0%) given that there are 2 responses out of the 10 patients. This would provide adequate evidence to suggest that additional studies with this agent may be warranted.

10 patients with metastatic BCC were planned in the expansion part of the study, but only 2 were enrolled due to early termination.

7. ANALYSIS POPULATIONS

The following analysis sets/populations will be used in this trial:

- **Safety population:** All enrolled patients who receive any amount of study drug. Unless otherwise noted, all safety analyses will be performed using Safety population.
- **Dose determining population:** All patients treated in the Phase 1 treatment-durationincrement part of the study. The dose determining population will be used to determine the primary outcome of the study, the RP2D dose.
- Efficacy population: All patients who are treated in the treatment-duration-increment cohort or the expansion cohort and whose pathologist's interpretation of baseline biopsy is consistent with BCC. Patients without interpretable baseline tissue, as determined by the pathologist, or by pathology report from the study site documenting a pathologist's determination of BCC will be excluded from the Efficacy population. Such patients' efficacy data will be presented in by-subject listings but excluded from all summary analyses. Objective response will be assessed separately for patients with mBCC vs. locally advanced BCC.
- **Relative Dose Intensity (RDI) population:** All patients treated in the expansion cohort including those who complete the protocol-defined treatment or discontinue treatment due to adverse events or for disease progression. Patients who are discontinued for any reason other than for adverse events or for disease progression will not be included in the relative dose intensity assessment. The RDI population will be used for the assessment of relative dose intensity defined for each cycle.

For some objectives (pharmacodynamics, biomarker parameters) a subgroup of patients of the efficacy population with respective baseline and post-baseline measurements will be used as described in section 11.9.1 below.

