7.2. BACKGROUND ON THE MOLECULE

7.3. RATIONALE FOR DOING THIS STUDY

7.4. DOSING REGIMEN AND STARTING DOSE

CX-4945 will be administered twice a day on a continuous basis. Each cycle will be 28 days (4 weeks) in duration and the first cycle will be used as the DLT observation period.

The starting dose will be 1000 mg BID (2000 mg total daily dose). This starting dose is based on three completed Phase I studies where patients were administered CX-4945 following a twice-daily (BID) or four-times-daily (QID) dosing regimen for 21 days followed by 7 days of rest. A total of 12 patients were treated at the 1000 mg bid dose level. Grade 3 or greater hypokalemia and hyponatremia associated to CX-4945 were reported but no drug-related severe diarrhea was noted. At the 1000 mg bid dose level, 1 out of 12 patients had DLT, grade 4 hypokalemia.

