9. INVESTIGATIONAL PLAN

9.1. STUDY DESIGN AND PLAN

This is an open label, multicenter, treatment duration increment trial Phase I runin study followed by two expansion cohorts to evaluate the safety, pharmacodynamic and preliminary antitumor activity of CX-4945 in patients with advanced basal cell carcinoma. All patients will receive CX-4945 until evidence of progression, intolerable toxicities most probably attributable to CX-4945, or withdrawal from the study. Day 1 of the study will be defined as the first day a patient receives CX-4945 (for the list of study assessments, please see the Study Flowchart in Appendix A).

This study population will consist of patients ≥ 18 years old with a histologically confirmed diagnosis of advanced BCC (metastatic BCC [mBCC] or locally advanced BCC as defined as follows) which has progressed on smoothened

inhibitor or that are intolerant to smoothened inhibitor (see Section 10.1.1, Inclusion Criteria).

Patients with mBCC are required to have histologic confirmation of a distant BCC metastasis (e.g., lung, liver, lymph nodes, or bone).

Patients with locally advanced BCC are required to have disease that is considered inoperable or to have a medical contraindication to surgery (see Section 10.1.1, Inclusion Criteria).

Patients with nevoid BCC syndrome (Gorlin syndrome) may enroll in this study but must meet the criteria for locally advanced or metastatic disease listed above.

In the phase I treatment duration increment part of the study, the 28-day continuous dosing of CX-4945 [1000 mg twice daily] will be explored. Dose cohort will initially include a minimum of 3 patients. A standard 3+3 design will be used. If no DLTs are seen in the 3 patients, the treatment duration increment part will be closed and the expansion cohorts will be opened.

If 1 patient out of 3 experiences a dose-limiting toxicity (DLT), up to 3 additional patients will be recruited (for a maximum of 6). If there are < 2/6 patients with DLT, this will be declared the dose for the Recommended Phase II Dose (RP2D), the Phase I will be closed and two expansion cohorts will be opened. If 2 out of 3, or 2 out of 6, patients experience DLT, the previous Phase I oral dosing regimen of 1000 mg BID (total daily dose 2000 mg) for 21 days followed by 7 days of rest will be selected for the expansion cohorts. The expansion cohorts will include 10 patients with locally advanced BCC and 10 patients with metastatic BCC.

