10.4. PATIENT REPLACEMENT

If a patient is not evaluable for toxicity for Cycle 1, that patient will be replaced to ensure the minimum number of patients are evaluable. Patients must receive $\geq 75\%$

planned dose to be considered evaluable for toxicity unless study drug was held or discontinued for toxicity and/or DLT has occurred.

All patients who are removed from the study for any reason other than for adverse events or for disease progression (e.g., voluntary discontinuation at the patient's request, or a severe violation of the study protocol) will be replaced. Data from these removed patients will be included in the overall safety analysis but will not be included in the assessment of relative dose intensity.

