11.11 Safety Analysis

Safety will be summarized over the Safety population unless indicated otherwise.

11.11.1Recommended Phase 2 Dose (RP2D)

The primary endpoint for this study is the determination of RP2D in the 28-day continuous dosing of CX-4945 [1000 mg twice daily] of the phase I treatment-duration-increment part of the study, as following:

- If no DLTs are seen in the 3 patients, the treatment-duration-increment part will be closed and the expansion cohorts will be opened. This will be declared the dose for the RP2D.
- If 1 patient out of 3 experiences a DLT, up to 3 additional patients will be recruited (for a maximum of 6). If there are < 2/6 patients with DLT, this will be declared the dose for the RP2D, Phase I will be closed and two expansion cohorts will be opened.
- If 2 out of 3, or 2 out of 6, patients experience DLT, the previous Phase I oral dosing regimen of 1000 mg BID (total daily dose 2000 mg) for 21 days followed by 7 days of rest will be selected for the expansion cohorts.

The procedures and rules to determine the RP2D are given in Section 9.1 of the protocol and as described above. Because of the small number of patients involved in this endpoint, no summaries will be generated. The determination of the RP2D in the RP2D population (see Section 7) will be described textually.

11.11.2Dose Limiting Toxicity (DLT)

Dose limiting toxicity (DLT) will be defined as any of the following drug related adverse events occurring during Cycle 1 (first 28 days of dosing):

- Grade 3 or 4 non-hematologic toxicity (excluding inadequately managed nausea and vomiting, alopecia or grade 3 fatigue lasting < 7 days),
- Grade 4 myelosuppression ≥ 7 days, febrile neutropenia or ≥ grade 3 thrombocytopenic bleeding,

• Other toxicity of concern to the investigators including toxicities requiring delays ≥ 14 days.

All DLTs will be listed and summarized by cohort (treatment-duration-increment, expansion) and overall for the Safety population.

11.11.3Adverse Events

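### Should the SAP's dose determining population be limited to run-in patients evaluable for toxicity in Cycle 1?

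*SAP*

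**What the plan says.** SAP section 7 (Analysis Populations) defines the dose determining population as "All patients treated in the Phase 1 treatment-durationincrement part of the study", and adds: "The dose determining population will be used to determine the primary outcome of the study, the RP2D dose".

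Protocol section 10.4 (Patient Replacement) says that when a patient is not evaluable for toxicity in Cycle 1, "that patient will be replaced to ensure the minimum number of patients are evaluable". To be evaluable, a patient must receive at least 75% of the "planned dose to be considered evaluable for toxicity unless study drug was held or discontinued for toxicity and/or DLT has occurred".

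Protocol section 9.1 gives the 3+3 rule: "Dose cohort will initially include a minimum of 3 patients", with up to 3 more after one DLT. Protocol section 7.4 sets the observation window: "Each cycle will be 28 days (4 weeks) in duration and the first cycle will be used as the DLT observation period".

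SAP section 11.11.1 refers back to the protocol: "The procedures and rules to determine the RP2D are given in Section 9.1 of the protocol and as described above". It plans no RP2D summary. The determination is to be described in text, for what that section calls the RP2D population, with a pointer to section 7. SAP section 1 states: "This plan will not repeat all the definitions given in the protocol but will provide further details of the summaries and analyses planned therein".

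**The concern.** The RP2D is the primary endpoint, and a 3+3 decision is only as good as the patients counted in it. A patient who leaves after a few days for reasons unrelated to toxicity has not been observed long enough to show whether the schedule is tolerable. Protocol 10.4 deals with this by replacing such patients. SAP 7 appears to let them back in, because it asks only that the patient was treated.

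Three features make the gap look worse:

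- SAP 11.11.1 cites protocol 9.1 but not 10.4.
- The label in 11.11.1 does not match the one in section 7.
- The 75% condition that appears in SAP section 3 concerns only the first run-in patient.

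If non-evaluable patients filled places among the first three and were not replaced, the rule would accept a toxic schedule more often. If they were only added to the reported denominator, the run-in would look slightly safer than it was.

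**Working it through.** **1. The plan's own sizes.** The run-in starts with 3 patients and can add 3, so 3 + 3 = 6. This matches the approximately 3 to 6 in protocol 15.6 and SAP 6. Adding the expansion, 6 + 10 + 10 = 26 matches protocol section 18.

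**2. What a non-evaluable patient can contribute.** By the 10.4 definition, a patient with a DLT is evaluable whatever dose was received. The same holds for a patient whose drug was withheld or stopped because of toxicity. A non-evaluable patient therefore has no DLT. Write d for the number of DLTs, n for evaluable patients and k for treated but non-evaluable patients:

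- evaluable set: d of n
- all-treated set: d of (n + k)

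The count d is the same in both. The documents give no value for k; I assume 0 to 2.

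| Outcome in protocol 9.1 | k = 0 | k = 1 | k = 2 |
|---|---|---|---|
| no DLT in 3 | 0 of 3 | 0 of 4 | 0 of 5 |
| 1 DLT in 6 | 1 of 6 | 1 of 7 | 1 of 8 |
| 2 DLTs in 3 | 2 of 3 | 2 of 4 | 2 of 5 |
| 2 DLTs in 6 | 2 of 6 | 2 of 7 | 2 of 8 |

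The 9.1 rule is written for 3 and 6 patients. When 10.4 is followed, those 3 or 6 are the evaluable patients, and the decision in each row is the same across the columns. A treated count of 4, 5, 7 or 8 has no entry in the rule, so an analyst has to go back to the evaluable patients to apply it.

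**3. What would happen without replacement.** Let p be the DLT probability, with n1 and n2 patients effectively observed in the two stages. The probability of accepting the 28-day schedule is

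P = (1 − p)^n1 + n1 · p · (1 − p)^(n1 − 1) · (1 − p)^n2.

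The values of p are assumptions. The second column is the design with 3 + 3 observed; the third has one of the first three not evaluable and not replaced (2 + 3 observed).

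| p | 3 + 3 | 2 + 3 |
|---|---|---|
| 0.20 | 0.512 + 0.197 = 0.709 | 0.640 + 0.164 = 0.804 |
| 0.30 | 0.343 + 0.151 = 0.494 | 0.490 + 0.144 = 0.634 |
| 0.40 | 0.216 + 0.093 = 0.309 | 0.360 + 0.104 = 0.464 |

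This shows why 10.4 matters. It does not measure a fault in the SAP, because it requires 10.4 to be ignored while the trial is running.

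**4. When the decision is taken.** Under protocol 9.1 the expansion opens only once the run-in closes. SAP section 6 records that 2 of the 10 planned metastatic patients were enrolled in the expansion before early termination. The run-in decision therefore came before this SAP, under the protocol's rules, and a population definition in the SAP cannot alter it.

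**5. Whether evaluable patients can be identified from planned outputs.** SAP 11.6 defines cumulative dose per cycle from the diary, and its last line extends cumulative dose to the Safety population, which contains every treated run-in patient. SAP 10.1 puts derived variables used in summaries into by-subject listings. The threshold follows directly:

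- planned Cycle 1 dose: 28 days × 2 g/day = 56 g, or 56 / 0.2 = 280 capsules
- 75% of that: 0.75 × 56 = 42 g, or 210 capsules

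Relative dose intensity would be the wrong quantity, because it divides by days of dosing. A patient who takes full doses for 10 days and leaves has 100% intensity but 20 of 56 g (35.7%). Cumulative dose avoids this. DLTs are listed under SAP 11.11.2, and dispositions under 11.1.

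**The case for a change.** The strongest argument for a change is that SAP 7 is not silent. The statement in SAP 1 that protocol definitions are not all repeated can excuse an omission, but here a definition is given and it differs. SAP section 12 declares no significant change from the protocol, so the difference is not presented as deliberate. The effect is also one-sided: extra patients enter only the denominator, so 1 of 6 (16.7%) would read as 1 of 7 (14.3%) with one such patient. Since the primary endpoint is reported only in words, the reader depends on those words giving the right denominator.

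Part of this stands. The wording does differ, 10.4 is not cited beside 9.1, and the population has two names. The names cause no ambiguity, because only one population in section 7 is tied to the RP2D.

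The rest carries less weight. Protocol 10.4 is a replacement rule and defines no analysis set; the protocol's statistical section names only an all-treated population. That the 9.1 counts are in evaluable patients is a fair reading of 9.1 together with 10.4, but 9.1 does not say so. No RP2D percentage is planned, so 14.3% is not an output of the SAP 7 definition. A ratio of that kind could come only from the DLT summary in 11.11.2, which uses the Safety population. That is a legitimate choice, and it would stay the same under a narrower dose determining population. An all-treated set also cannot lose a DLT.

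**Conclusion.** No change to the plan is needed. The difference between SAP 7 and protocol 10.4 is real but editorial. Its full extent is one population count, if tabulated in the disposition summary, and one sentence describing the RP2D. Both are affected only if some run-in patient was treated but not evaluable. With none there is no effect; with an assumed 1 or 2, the count rises by 1 or 2, while the number of DLTs and the schedule chosen under 9.1 stay the same.

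This rests on two assumptions. The first is that replacement under 10.4 was followed during the run-in. The second is that whoever writes the RP2D text reads 9.1 together with 10.4 and states how many patients were evaluable, as is usual for a 3+3 cohort. The planned dose, DLT and disposition listings allow a reader to check that statement patient by patient. A narrower definition would add no information and protect no decision.

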8. HANDLING OF MISSING DATA

Missing data will not be replaced with imputed values.

